4.2 Secondary Endpoint

The secondary efficacy endpoint is the following:

- CFB (Day -7 through Day -1) in the average score of ocular discomfort and dryness on the [REDACTED] Ocular Discomfort & 4-Symptom Questionnaire at the bedtime assessment from the patient daily diary during Day 1 through Day 14
 - Each day during the at-home dosing period, patients will grade the severity of their DED symptoms in their diary before instilling the study drug at their morning and evening doses.
 - The [REDACTED] Ocular Discomfort & 4-Symptom Questionnaire will be used, which includes rating the severity of 5 symptoms: ocular discomfort, burning, dryness, grittiness, and stinging. Each symptom rating ranges from 0 to 5 using whole numbers, where 0 = None and 5 = Worst.
 - The CFB is calculated as the average score of ocular discomfort and dryness of the study day minus the baseline value (as defined in [Section 9.3](#))

4.2.1 STATISTICAL HYPOTHESES OF SECONDARY ENDPOINT

The statistical hypotheses are stated in terms of one-sided hypotheses, at a significance level of 0.025.

H_{02} : The CFB (Day -7 through Day -1) in the average score of ocular discomfort and dryness at the bedtime assessment from the Patient Daily Diary during Day 1 through Day 14 for 0.3% SI-614 is equal or greater than placebo.

H_{A2} : The CFB (Day -7 through Day -1) in the average score of ocular discomfort and dryness at the bedtime assessment from the Patient Daily Diary during Day 1 through Day 14 for 0.3% SI-614 is less than placebo.

4.3 Exploratory Endpoints

The exploratory efficacy endpoints are the following:

Signs:

- Fluorescein staining score on the [REDACTED]
 - [REDACTED]
 - [REDACTED]
 - [REDACTED] will also be derived and analyzed.
- Lissamine green staining score on the [REDACTED]
 - Lissamine green staining will be assessed in each eye at all visits for all [REDACTED] time points.
 - Grading of the [REDACTED] regions will be conducted using [REDACTED] Corneal and Conjunctival Staining Scale from 0 to 4 [REDACTED] where grade 0 = No Staining and 4 = Confluent Staining.
 - [REDACTED]
 - [REDACTED]

- [REDACTED] will also be derived and analyzed.
- Tear film break-up time (TFBUT)
 - TFBUT will be assessed in each eye at all visits for all [REDACTED] time points.
 - For each eye, two measurements will be recorded in seconds and averaged unless the two measurements are >2 seconds apart and are each <10 seconds, in which case, a third measurement will be taken and the two closest of the three will be averaged and used for analyses. If the differences between two sequential pairs of measurements are the same (e.g., 3, 6, 9 seconds), then the median of the three readings will be used for analysis.
- Conjunctival redness on [REDACTED] Scale
 - Conjunctival redness using the [REDACTED] Conjunctival Redness Scale will be assessed in each eye at all visits for all [REDACTED] time points.
 - The conjunctival redness scale ranges from 0 to 4 where 0 = Normal, [REDACTED]
[REDACTED]
[REDACTED] and
 - 4 = [REDACTED]

[REDACTED] Analyses will be for study eye only.

Symptoms:

- Patient daily diary during the dosing period
 - On each day during the at-home dosing period, patients will grade the severity of their DED symptoms in their diary in the morning and in the evening before instilling the study drug. [REDACTED] Ocular Discomfort & 4-Symptom Questionnaire will be used, which includes rating the severity of 5 symptoms at the subject level: ocular discomfort, burning, dryness, grittiness, and stinging. Each symptom rating ranges from 0 to 5, where 0 = None and 5 = Worst.
- Ocular Surface Disease Index (OSDI) questionnaire
 - The OSDI is assessed on a scale of 0 to 100, with higher scores representing greater disability. The OSDI asks the following 12 questions at the subject level:

Have you experienced any of the following during the last week:

- (1) Eyes that are sensitive to light?
- (2) Eyes that feel gritty?
- (3) Painful or sore eyes?
- (4) Blurred vision?
- (5) Poor vision?

Have problems with your eyes limited you in performing any of the following during the last week:

- (6) Reading?
- (7) Driving at night?
- (8) Working with a computer or bank machine (ATM)?
- (9) Watching TV?

Have your eyes felt uncomfortable in any of the following situations during the last week:

- (10) Windy conditions?
- (11) Places or areas with low humidity (very dry)?
- (12) Areas that are air conditioned?

The OSDI will be assessed at each visit, including all [REDACTED] time points. The total OSDI score is calculated by the following:

$$\text{OSDI} = \frac{(\text{Sum of Scores}) \times 25}{\# \text{ of Questions Answered}}$$

Note that the number of questions answered in the denominator should exclude questions with a response of "N/A". OSDI will be analyzed for total OSDI score and subtotal scores (i.e., OSDI questions 1-5, OSDI questions 6-9, and OSDI questions 10-12).

- [REDACTED] Ocular Discomfort and 4-Symptom Questionnaire
 - As described in the assessment description for the "Patient daily diary during the dosing period" endpoint
- [REDACTED] Ocular Discomfort Scale
 - Ocular discomfort will be assessed in each eye using the [REDACTED] Ocular Discomfort Scale at all visits, including [REDACTED] time points.
 - For the [REDACTED] time point, patients will rate their ocular discomfort [REDACTED]
[REDACTED] [REDACTED]
[REDACTED] [REDACTED] The Ocular Discomfort Scale ranges from 0 to 4 where 0 = No discomfort, [REDACTED]
[REDACTED] and 4 = Constant discomfort.

4.4 Safety Variables

The safety endpoints include the following:

- AEs
- Best-corrected visual acuity (BCVA)
 - The logarithm of the minimum angle of resolution (logMAR) BCVA will be assessed [REDACTED] [REDACTED] at each visit, as well as [REDACTED] at Visit 3 (Day 8), using an Early Treatment of Diabetic Retinopathy Study (ETDRS) chart. Patients should use their most recent correction to attain their BCVA.

- Slit-lamp biomicroscopy
 - A slit-lamp biomicroscopy examination of the cornea, conjunctiva, anterior chamber, iris, lens, and lid will be performed at each visit, including all [REDACTED] time points. The examination consists of a categorical determination of each region graded as Normal, Abnormal Not Clinically Significant (NCS), or Abnormal Clinically Significant (CS).

5 Study Treatments

5.1 Method of Assigning Patients to Treatment Groups

Each subject who meets all the inclusion and none of the exclusion criteria at Visit 1 (Day -14) and Visit 2 (Day 1) will be assigned a randomization number at the end of Visit 2 (Day 1). The Interactive Web Response System (IWRS) will be used to assign all randomization numbers and kit numbers will be to each subject as they are entered into the IWRS.

The site staff will dispense each kit required until the next visit. Both the randomization number and the dispensed study drug kit number will be recorded on the subject's source document and electronic case report form (eCRF).

5.2 Masking and Unmasking

All patients, investigators, and study personnel, including Sponsor, [REDACTED] and [REDACTED], involved with the conduct of the study will be masked with regard to treatment assignments. When medically necessary, the investigator may need to determine what treatment group has been assigned to a subject. When possible (i.e., in non-emergent situations), [REDACTED] and/or the study Sponsor should be notified before unmasking study drug. [REDACTED] and/or the study Sponsor must be informed immediately about any unmasking event.

If an investigator identifies a medical need for unmasking the treatment assignment of a subject, they should contact [REDACTED] and/or the medical monitor prior to unmasking the identity of the investigational product (IP), if possible. [REDACTED] will ask the site to complete and send them the Unmasking Request Form. [REDACTED] will notify the Sponsor and jointly will determine if the unmasking request should be granted. They may consult the medical monitor as needed. The result of the request will be documented on the Unmasking Request Form. The investigator will unmask the subject's treatment assignment using IWRS upon approval of request. The investigator will complete the Unmasking Memo form and include it in the subject's study file and provide a copy for the Trial Master File (TMF). For each unmasked request, the reason, date, signature, and name of the person who unmasked the subject must be noted in the subject's study file.

Unmasked patients will be discontinued from the study. Unmasked patients will be followed for safety monitoring until resolution of the AE or study completion, whichever occurs last.

6 Sample Size and Power Considerations

In order to detect a difference of -0.75 for the primary endpoint between 0.3% SI-614 and placebo with 90% power and accounting for an assumed 5% drop-out rate, 115 patients are required to be randomized per treatment group. This assumes a two-sided test at alpha = 0.05 and a common standard deviation (SD) of 1.7.

The power and sample size for this study were calculated and based upon the results from the previous Phase 2 (Protocol # 614/1121) and Phase 2/3 study (Protocol # 614/1131).

7 Data Preparation

7.1 Input Data

Study data will primarily be recorded on the eCRFs supplied by [REDACTED] using [REDACTED]

When all prerequisites for database lock have been met, the database will be locked. Following database lock, approval will be obtained from the Sponsor to unmask the study. Any changes to the database after data have been locked can only be made with the approval of the Sponsor in consultation with [REDACTED].

Final analysis will be carried out after the following have occurred:

- Database lock has occurred with written authorization provided by appropriate [REDACTED] and Sponsor personnel.
- Protocol deviations have been identified and status defined (major/minor deviations) prior to database lock.
- Analysis populations have been determined.
- Randomized treatment codes have been unmasked.

7.2 Output Data

Data from Electronic Data Capture (EDC) will be transferred to Biostatistics and incorporated into standard formats following the Study Data Tabulation Model (SDTM). Data will then be mapped to analysis datasets using the Analysis Data Model (ADaM). Both SDTM- and ADaM-formatted data will be used to create the subject listings, while all tables and figures will be based on the ADaM-formatted data.

SDTM will follow the SDTM version 1.7 model and will be implemented using the SDTM Implementation Guide version 3.3 and the SDTM Controlled Terminology version 2022-03-25. ADaM data will follow the ADaM version 2.1 model and will be implemented using the ADaM Implementation Guide version 1.1. Both SDTM and ADaM will be validated using Pinnacle 21. Any discrepancies in the validation will be noted in reviewer's guides accompanying the final data transfers.

Define.xml will be created for SDTM and ADaM using the Define-XML version 2.0 model.

8 Analysis Populations

8.1 Intention-to-Treat Population

The Intention-to-Treat (ITT) population includes all randomized patients. Patients in the ITT population will be analyzed as randomized.

8.2 Per-Protocol Population

The Per-Protocol (PP) population is defined as all ITT patients who have no major protocol deviations and who complete the trial. Protocol deviations will be assessed prior to database lock and unmasking. Patients in the PP population will be analyzed as treated.

8.3 Safety Population

The Safety population includes all randomized patients who have received at least one dose of study drug. Patients in the Safety population will be analyzed as treated.

9 General Statistical Considerations

9.1 Unit of Analysis

Safety endpoints will be analyzed for both eyes. For efficacy endpoints, the unit of analysis will be the study eye, as defined by the following:

Study Eye: Eyes are eligible for analysis if they meet all inclusion criteria. In the case that both eyes are eligible for analysis, the study eye will be the eye with the greatest change from [REDACTED] to [REDACTED] (i.e., [REDACTED] minus [REDACTED] in corneal total fluorescein staining score (sum of [REDACTED] regions) at baseline (Visit 2). If the baseline change from [REDACTED] to [REDACTED] in corneal total fluorescein staining score is the same in both eyes, then the right eye will be used as the study eye. If only one eye meets all inclusion criteria, then the single qualifying eye is the study eye.

9.2 Missing or Inconclusive Data Handling

Missing data for the primary efficacy endpoints will be imputed as specified as follows:

- For MAR, the data will be imputed using treatment-group based MCMC on the ITT population
- For MNAR due to intercurrent events, the imputation methods are defined in [Section 4.1.2](#) for estimands.

The rate of intercurrent events for primary efficacy endpoint will be summarized by treatment group and overall, with Fisher's exact test p-value.

Imputation of missing data will be executed for partial or missing dates where complete dates are required to flag data as treatment-emergent or concomitant with treatment. Partial/missing start and end dates for AEs and concomitant medications will be imputed as follows:

Partial/missing start date:

- Dates with missing day only will be imputed as the 1st of the month unless the month and year are same as the month and year of first dose of study medication, in which case missing day will be imputed as the first dose day of study medication.
- Dates with both day and month missing will be imputed as 1 Jan unless the year is same as the year of first dose of study medication, in which case missing day and month will be imputed as the first dose day and month of study medication.
- Completely missing dates will be imputed as the first dose date of study medication unless the end date is on or before the first dose date of study medication, in which case missing date will be imputed as 1 Jan of the same year as the end date.

Partial/missing end date:

- Dates with missing day only will be imputed as the last day of the month unless the month and year are the same as the month and year of the last dose of study medication, in which case missing day will be imputed as the last dose day of study medication.
Dates with both day and month missing will be imputed as 31 Dec unless the year is same as the year of the last dose of study medication, in which case missing day and month will be imputed as the last dose day and month of study medication.
- If the ongoing flag is missing or “Yes” then the date will not be imputed unless death date is available, in which case the missing date will be imputed as the death date. If ongoing is “No” then the missing end date will be imputed as the last dose date.
- If the imputed date is after the date of death, then the end date will be set equal to the date of death.

The original dates will be displayed in data listings, and the imputed dates will be used in derivations only (study day, treatment-emergence status, etc.).

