15.1 Adverse Events

An AE is defined as any untoward medical occurrence associated with the use of a drug in humans, whether or not the event is considered drug-related. An AE can therefore be any unfavorable and unintended sign (e.g., an abnormal laboratory finding), symptom, or disease occurring after the patient started dosing with the study drug, without any judgment about causality. Any pre-existing medical condition that worsens after first administration of the study drug will also be considered a new AE. The AE reporting period ends upon study exit. Study drug includes the investigational drug under evaluation and any comparator drug, vehicle,

or any other medications required by the protocol given during any stage of the study. All AEs will be coded using MedDRA Version 25.0.

Treatment-emergent adverse events (TEAEs) are defined as any event that occurs or worsens after the first dose of randomized study treatment.

Severity of an AE is defined as a qualitative assessment of the degree of intensity of an AE as determined by the Investigator or reported to them by the patient. The assessment of severity is made irrespective of relationship to study drug or seriousness of the event and should be evaluated according to the following scale:

- *Mild*: Event is noticeable to the subject, but is easily tolerated and does not interfere with the subject's daily activities.
- *Moderate*: Event is bothersome, possibly requiring additional therapy, and may interfere with the subject's daily activities.
- *Severe*: Event is intolerable, necessitates additional therapy or alteration of therapy, and interferes with the subject's daily activities.

The relationship of each AE to the study drug should be determined by the Investigator using these explanations:

- *Suspected*: A reasonable possibility exists that the study drug caused the AE.
- *Not Suspected*: A reasonable possibility does not exist that the study drug caused the AE.

An overall summary will be presented that includes the number of events and the number and percentage of patients who experienced at least one TEAE, as well as breakdowns of TEAEs further categorized by ocular and non-ocular, severity, relationship to study drug, seriousness and reasons for seriousness, and the number of patients with TEAEs causing premature treatment discontinuation.

In addition to the overall AE summary, summaries will be provided for the following categories of AEs:

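### Two of the three start-date rules in SAP 9.2 lack an end-date check, so a partly dated run-in event that ended before Visit 2 gets an onset after its own end

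*SAP*

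**What the plan says.** SAP 9.2 gives three rules for incomplete start dates of adverse events and concomitant medications.

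- Day missing: use the 1st of the month, unless month and year match those of the first dose, "in which case missing day will be imputed as the first dose day of study medication".
- Day and month missing: use 1 January, unless the year matches that of the first dose, "in which case missing day and month will be imputed as the first dose day and month of study medication".
- Completely missing: use the first dose date, "unless the end date is on or before the first dose date of study medication". In that case use 1 January of the end-date year.

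Only the third rule looks at the end date. Nothing later in the section caps a start date at its end date; the only cap is on end dates, at death. The section closes by keeping the original dates in the listings and using the imputed dates for derived variables, and it names treatment-emergence status among them.

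SAP 15.1 defines a treatment-emergent event as "any event that occurs or worsens after the first dose of randomized study treatment". SAP 12.2 likewise ties concomitant medications to the randomized drug. SAP 9.2 refers to *study medication* and does not define it.

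**The concern.** Run-in events are collected: Protocol 8.3.1 has an adverse-event query at Visit 1 and another at the start of Visit 2. Such an event may be recorded with an incomplete start and a known end before Visit 2. The first two rules then move its start to the first dose date, because nothing tells the programmer to look at the end date. The result is an interval that ends before it begins.

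Every adverse-event table planned in SAP Section 21 (Tables 14.3.1.1 to 14.3.1.9) is limited to treatment-emergent events. The imputed start therefore helps decide whether an event is tabulated at all. A medication stopped before Visit 2 can in the same way be given a Day 1 start, and would look concomitant to a program that tests only the start date.

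**Working it through.** The plan states no figure to reproduce here. The check applies the rules as written, then asks how often the calendar condition is met.

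**Worked case** (illustrative dates). Visit 2 and first randomized dose on 10-JUN-2022; event ended 05-JUN-2022.

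| Recorded start | Imputed start | Against end date | Treatment-emergent? |
|---|---|---|---|
| UNK-JUN-2022 | 10-JUN-2022 | 5 days after | Yes, if Day 1 onset counts |
| UNK-UNK-2022 | 10-JUN-2022 | 5 days after | Yes, if Day 1 onset counts |
| Completely missing | 01-JAN-2022 | before | No |

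The record with the least information gets the most sensible result, which points to an oversight in the first two rules.

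**Inputs for the frequency**

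- Run-in length L = 14 days (Protocol 4). The ±3-day window at Visit 1 gives 11 to 17 (SAP Table 1).
- Assumptions: Visit 2 is spread evenly over 365 days; onset is spread evenly over the run-in; the event lasts D = 1, 3 or 5 calendar days; the first dose is the Visit 2 dose.
- Events considered: those that ended before Visit 2. With onset k days before Visit 2, this means k runs from D to L.

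**Formula.** For a given k, onset falls before a given month boundary on exactly k Visit 2 dates (days 1 to k of the month). Summing k from D to L gives (L − D + 1)(L + D)/2 combinations per boundary, out of 365 × (L − D + 1). The share that crosses one boundary is therefore (L + D)/730. There are 12 month boundaries and one year boundary, so the share re-dated to a day after the event ended is:

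- day missing: 1 − 12(L + D)/730
- day and month missing: 1 − (L + D)/730
- completely missing: 0, because of the end-date exception

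**Results for L = 14**

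| D (days) | Day missing | Day and month missing |
|---|---|---|
| 1 | 1 − 180/730 = 75.3% | 1 − 15/730 = 97.9% |
| 3 | 1 − 204/730 = 72.1% | 1 − 17/730 = 97.7% |
| 5 | 1 − 228/730 = 68.8% | 1 − 19/730 = 97.4% |

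Over run-ins of 11 to 17 days, the day-missing share runs from 1 − 12 × 22/730 = 63.8% (L = 17, D = 5) to 1 − 12 × 12/730 = 80.3% (L = 11, D = 1). The day-and-month share runs from 97.0% to 98.4%. A direct enumeration of all 365 Visit 2 dates with the rules coded literally gives the same values.

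**Same-day rule.** The treatment-emergent flag in the worked case needs onset on the Visit 2 date to count. SAP 15.1 speaks of events after the first dose and gives no rule for the same date. Under a strict later-than comparison of dates the event would not be flagged, but its start would still fall after its end.

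**The case against.** The best defence is the sentence in SAP 9.2 that introduces the rules. It limits imputation to cases where a complete date is needed to set a flag. An event known to have ended before Visit 2 cannot be treatment-emergent, so arguably its start needs no imputation. That shows the intent, but it does not repair the text. If the sentence settled such cases, the explicit exception in the third rule would be unnecessary.

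It is also fair that the harm is limited. Adverse-event queries at Visits 1 and 2 should make run-in events with both day and month missing rare. Listings of all adverse events keep the original dates. For a medication, a known stop date before Visit 2 settles its status under SAP 12.2 unless the program ignores that date. All of this stands and bears on severity.

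A reader might infer three stronger points that the documents do not support.

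1. *The rules also drop genuine on-treatment events.* SAP 15.1 says "Study drug includes the investigational drug under evaluation and any comparator drug, vehicle", and it extends this to protocol-required products at every stage. If the anchor in SAP 9.2 were the run-in vehicle dose at Visit 1, some post-randomization events would be dated back to Visit 1. But both flags served by these rules are tied to randomized drug. Protocol 8.3.1 calls the Visit 1 dose run-in solution and treats the Visit 2 dose as the first of study drug. SAP 13 lists run-in and study drug separately, and SAP 13.1 and 13.2 count from Visit 2. The run-in reading is unlikely. Nor can the two errors occur together: in the enumeration each anchor gave 0% for the other's error. What remains is loose wording.
2. *The end-date rules corrupt the tables too.* A partial end date in the month of the last dose can be set before a known later start. That is untidy, but an event or medication starting after the last dose is already after the first randomized dose. No flag changes, and no analysis of event duration is planned.
3. *About three quarters of run-in events are misdated.* The percentages apply only to events with a partial start date and a known end before Visit 2. For events still ongoing at Visit 2, dating to the first dose is the usual conservative convention.

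**Conclusion.** Wrong as written, but minor. Read literally, the day-missing and day-and-month-missing rules give an onset after the event's own end for most ended run-in events to which they apply: 69% to 75% and 97% to 98% respectively with a 14-day run-in and events of 1 to 5 days. The start-after-end fault rests on the Visit 2 anchor. The false treatment-emergent flag also needs Day 1 onset to count.

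The documents give no number of partial dates, so the number of affected events cannot be stated; it is probably small. The affected events precede randomization, so the over-count should not differ by arm, and the documents give no ground for calling the between-arm safety comparison biased. No efficacy result depends on these dates.

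**What to change.** In SAP 9.2:

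1. Replace the reference to the first dose of study medication with *first dose of randomized study drug (Visit 2)* throughout the start-date rules. This matches SAP 12.2 and 15.1 and closes the anchor question.
2. Add to the first two start-date rules: if a known end date is before that dose, impute the 1st of the month (day missing) or 1 January (day and month missing). In the worked case this gives 01-JUN-2022 or 01-JAN-2022, both before the end date. An event that ends on the Visit 2 date keeps its Day 1 start, which is a possible interval. Otherwise leave the completely-missing rule as it is, because it already works.

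Optional, with no effect on any flag: state that an imputed end date is never earlier than the start date.

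The cost is two sentences, or three with the optional one, and a few lines of derivation code, to be settled before database lock. No new data are needed.
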